8.3 Statistical Analyses

Primary Analysis

The relationship between time-matched, baseline-adjusted QTcF (dQTcF) and moxidectin concentrations will be investigated by linear mixed-effects modeling. The ddQTcF value will be calculated as the placebo-corrected dQTcF estimated from the model.

Before modeling, the concentration-ddQTcF relationship will be explored graphically to determine the presence of hysteresis. Hysteresis will be assumed if, on average (or median), there are at least 3 time points with ddQTcF >5 msec and the time to maximum observed plasma concentration (T_{max}) and the time of maximal ddQTcF (U_{max}) differ by 30 minutes or more and the 1-sided, 1-sample Wilcoxon test for the difference between ddQTcF at T_{max} and at U_{max} is significant at the 1% level. If hysteresis is present, the possibility of fitting a population PK model with an effect compartment will be explored.

The primary analysis will be provided for the ECG population using a mixed-effects model with dQTcF as the dependent variable and treatment (active and placebo), time point, and treatment by time point interaction as the independent variables with baseline QTcF as a covariate and time-matched concentrations of moxidectin (observed if hysteresis is not present; predicted from the effect compartment if hysteresis is present) as a covariate with random effects of intercept and slope. Concentrations of zero will be used for the placebo treatment. A spatial power law covariance structure (a time-dependent first-order autoregressive covariance designed for unequally-spaced time points) will be used. If the model does not converge then unstructured (UN) or compound symmetry (CS) structures will be assessed, in that order. The model will be used for predicting population average and 90% 2-sided bootstrapped CI of the baseline-adjusted difference (ie, ddQTcF) between active and placebo at each time point bound at clinically relevant concentrations. The bootstrap method will be based on percentile CI using the 5th and 95th percentiles in the resampling distribution using 1000 iterations.

The criterion for negative QT assessment will be the upper bound of the 2-sided 90% bootstrapped CI for ddQTcF being below 10 msec at the largest geometric mean C_{max} value. In addition, the significance and magnitude of parameter estimates of the treatment covariate (active vs. placebo) will be considered.

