At the request of the United States Food and Drug Administration, the primary endpoint in the study has been updated to dQTcF and this is the dependent variable in the primary analysis, which includes plasma concentrations as covariates with random slope and intercept as well as treatment and time point as categorical independent variables. However, in addition to obtaining the plasma concentration intercept and slope estimates, the estimated dQTcF values from the primary analysis will be compared by calculating the differences overall and at each time point between the active treatment and placebo, resulting in estimates of ddQTcF, which will be presented. In addition, a secondary analysis with ddQTcF as the dependent variable will be performed, as is typical and well understood, to assess correlation and overall profile of ddQTcF and plasma concentrations. We believe it is important to do these analyses in addition to the primary analysis, because the dQTcF analysis could yield a spuriously positive or negative regression slope based on the relationship between the well-known spontaneous circadian change in dQTcF and the concentration-time profile of the investigational drug. For example, if the early to midday circadian increase in dQTcF concurred with a rise in plasma concentration of moxidectin, this could create the appearance of a positive relationship that might exceed the upper confidence boundary of 10 msec within the drug's clinically-expected concentration range. Converse timing between circadian change and plasma concentration change could produce the opposite effect. In the ddQTcF analysis, the placebo group's circadian change largely eliminates this type of spurious observation. Thus, in addition to examining the dQTcF model, if the primary analysis produces a significantly positive or negative regression slope, we will also examine the relationship between the investigational drug's plasma concentration-time course in relationship to the circadian change of dQTcF in the placebo group, to determine if a positive or negative correlation could have affected the dQTcF-plasma concentration relationship.

The relevant SAS code statements are:

```
PROC MIXED DATA = DATA;  
  CLASS SUBJID TRT ATPTN;  
  MODEL dQTcF = BASE TRT ATPTN TRT*ATPTN CONC /SOLUTION  
RESIDUAL OUTP=PRED;  
  RANDOM INTERCEPT CONC / SUBJECT = SUBJID;  
  REPEATED ATPTN / type=SP(POW) (ATPTN) SUBJECT=SUBJID;  
  LSMEANS TRT TRT*ATPTN /DIFF ALPHA=0.1 CL at CONC=xx.x;  

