The adequacy of the linear assumption between ddQTcF and plasma concentrations will be determined by adding a quadratic term to the mixed-effects model. If the quadratic term is different than zero, having $P < 0.05$, and Akaike's information criterion (AIC) is smaller in comparison with the linear model's AIC, then a quadratic term may be added. In addition, a transformation of the concentrations (eg, $\log[C/LLOQ]$, where LLOQ is the lower limit of quantitation of the assay and all values below the LLOQ are replaced with the LLOQ) may also be assessed. The best model fit will be determined by the lowest AIC.

The predicted mean expected ddQTcF and the 90% 2-sided CI will be calculated using the estimates of the slopes from the mixed-effect models, for all subjects, at relevant concentration levels (ie, the mean maximum plasma concentration under each dose level).

The relevant SAS code statements are:

```
PROC MIXED DATA = DATA;  
  CLASS SUBJID;  
  MODEL ddQTcF = CONC /SOLUTION OUTPM=PRED ALPHA=0.05;  
  RANDOM INTERCEPT CONC / TYPE=UN SUBJECT = SUBJID;  
RUN;
```

In the above statements:

- CONC represents the measured plasma concentrations of moxidectin;
- Type=UN means an unstructured covariance matrix, which is used for the correlated random effects (INTERCEPT and CONC). If the model does not converge other covariance structures will be investigated.

A plot will be provided to show CI of each treatment using the following model, adding in the treatment variable as follows:

```
PROC MIXED DATA = DATA;  
  CLASS SUBJID TRT;  
  MODEL ddQTcF = CONC TRT/SOLUTION OUTP=PRED;  
  RANDOM INTERCEPT CONC /TYPE=UN SUBJECT = SUBJID;  
RUN;
```

Where TRT represents the individual treatments (moxidectin 4 mg, moxidectin 8 mg, moxidectin 16 mg, moxidectin 24 mg, and moxidectin 36 mg).

A plot of the observed median-decile drug concentrations and associated mean ddQTcF (90% CI) together with the mean model-predicted ddQTcF will be used to evaluate the adequacy of the model fit to the assumption of linearity and the impact on quantifying the concentration response relationship.

Categorical QTc Findings

Categorical summaries using the largest postdose QTcF and largest change from Baseline (dQTcF) will be performed to determine the number and percentage of subjects, by treatment, who meet each of the following criteria:

- Result ≤ 450 msec;
- Result > 450 and ≤ 480 msec;
- Result > 480 and ≤ 500 msec;
- Result > 500 msec;
- dQTcF ≤ 30 msec;

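### The primary model fixes the intercept–slope covariance at zero while both secondary models leave it free; if the two effects are correlated, ddQTcF at Cmax loses a little precision

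*SAP*

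**What the plan says.** All of this is in SAP Section 8.3.

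- **Primary analysis, prose.** Concentration enters "as a covariate with random effects of intercept and slope". No covariance structure is named for these two effects.
- **Primary analysis, code.** The statement is "RANDOM INTERCEPT CONC / SUBJECT = SUBJID". The residual structure is given separately: "REPEATED ATPTN / type=SP(POW) (ATPTN) SUBJECT=SUBJID". The fallback to unstructured or compound symmetry is attached to that residual structure and applies only if the model does not converge.
- **Secondary analysis, code.** Both models use "RANDOM INTERCEPT CONC / TYPE=UN SUBJECT = SUBJID", and the note says "Type=UN means an unstructured covariance matrix, which is used for the correlated random effects (INTERCEPT and CONC").
- **Decision rule.** "The criterion for negative QT assessment will be the upper bound of the 2-sided 90% bootstrapped CI for ddQTcF being below 10 msec", evaluated at the largest geometric mean Cmax. On the interval: "The bootstrap method will be based on percentile CI using the 5th and 95th percentiles in the resampling distribution using 1000 iterations". The significance and size of the treatment term are to be considered as well.

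**The concern.** Without `TYPE=`, PROC MIXED estimates a variance for the intercept and one for the slope and sets their covariance to zero. By Section 2.4.2, ddQTcF is dQTcF minus the placebo mean at the same time point, and that mean is the same for every active subject at that time. Apart from the other model terms, an active subject's intercept and slope are therefore the same quantities in the primary and secondary models. The SAP calls them correlated in one and forces them to be uncorrelated in the other.

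The existing fallback does not cure this, because a primary model that converges keeps the zero covariance. Nor is zero a neutral choice. Concentration is not centred, so the restriction is imposed at concentration zero, and moving the origin would change the fitted model.

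At stake is the precision of ddQTcF at Cmax, the quantity judged against 10 msec, and the accuracy of the model-based standard errors behind the treatment term and the LSMEANS limits.

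**Working it through.** **1. The plan's own figure.** No stated number depends on this point. The only sizing figure, 900 pairs (Section 3.2), reproduces as 6 × 10 × 15 (baseline plus 14 postdose times). The primary model uses the 14 postdose times.

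**2. What the restriction does.** Measure concentration c in units of the top-dose Cmax. The random effects give an active subject the variance

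s0² + 2ρ·s0·s1·c + s1²·c².

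The SAP gives no variance components, so take s0 = 5 and s1 = 8 msec as assumptions. At c = 1:

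- ρ = 0: 25 + 64 = 89
- ρ = −0.8: 25 − 64 + 64 = 25
- ρ = +0.8: 25 + 64 + 64 = 153

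The coded structure has no term for the ±64 and must absorb it in the other parameters. On the origin: if intercept and slope are uncorrelated at c = 0, the subject's level at c = 1 and the slope have correlation s1²/(s1·√(s0² + s1²)) = 64/(8 × 9.43) = 0.85.

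**3. Effect on ddQTcF at Cmax.** The fixed effects were those of the SAP's code, on 60 subjects × 14 postdose times. The contrast was the time-averaged active-minus-placebo effect plus slope × Cmax, with placebo at zero concentration. Assumptions: residual SD 6 msec with spatial-power correlation, and intercept SD 5 msec.

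| Method | Slope SD at Cmax | ρ | As coded (msec) | With UN (msec) | Ratio |
|---|---|---|---|---|---|
| Large-sample SE | 8 | −0.8 | 2.58 | 2.45 | 1.05 |
| Large-sample SE | 8 | +0.8 | 3.24 | 3.16 | 1.03 |
| REML simulation, 350 runs | 8 | −0.8 | 2.64 | 2.44 | 1.08 |
| REML simulation, 350 runs | 8 | +0.8 | 3.27 | 3.25 | 1.01 |
| REML simulation, 350 runs | 8 | 0 | 2.96 | 2.98 | 0.99 |
| Second REML simulation, 458–519 runs | 10 | −0.8 | 2.72 | 2.45 | 1.11 |
| Second REML simulation, 458–519 runs | 10 | +0.8 | 3.57 | 3.41 | 1.05 |

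The 1.01 and 0.99 are within simulation error. Bias was about zero in the 350-run simulations. In the second set, ρ = ±0.6 with slope SD 5 gave a gain of only 1–2% from 120 runs.

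A wider large-sample grid used intercept SD 3–7, slope SD 3–10 and residual SD 4–8 msec, with dose-proportional concentrations and 30–60% between-subject CV. The ratio was 1.000–1.004 at |ρ| = 0.2, 1.001–1.028 at 0.5, and 1.004–1.146 (median 1.022) at 0.9.

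**4. On the scale of the decision.** With a normal approximation, the upper 90% limit moves by 1.645 × the change in SE:

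- 2.45 to 2.58: 1.645 × 0.13 = 0.21 msec
- 2.44 to 2.64: 1.645 × 0.20 = 0.33 msec
- 2.45 to 2.72: 1.645 × 0.27 = 0.44 msec

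**5. Model-based SE of the treatment effect, as coded.** In the second simulation it was 1.68 against a true 1.83 at ρ = −0.8 (1.68/1.83 = 0.92, 8% too small). At ρ = +0.8 it was 2.21 against 1.89 (1.17, 17% too large, the most extreme case). A large-sample check gave 6–14% too small at negative ρ and 4–8% too large at positive ρ. For ddQTcF at Cmax itself, the model-based SE was 0.92–1.12 times the true SE over the grid.

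**6. Where the loss arises.** Placebo concentrations are zero and treatment-by-time is saturated. With complete data, all placebo subjects share one covariance matrix, and their time means are simple averages under either structure, apart from the baseline adjustment. With SDs 5, 10 and 6, the placebo contribution to the variance was 2.87 msec² under both, with a weight of about 0.1 per subject. The loss therefore comes from the weighting of the active arm.

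**The case against.** **The two models differ.** The secondary model has no residual correlation, baseline or time terms, so its random effects carry all the within-subject correlation. The primary model has those terms, and its spatial-power residual may absorb part of any subject-level drift. The SAP's note on correlated effects is written for the secondary code, and the primary prose does not conflict with the primary code. This stands in part. A reader might infer a formal contradiction, but the documents show only an unexplained difference. It still matters, because the SAP expects a correlation in these effects and gives no reason for setting it to zero in the model that decides.

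**The large figures need strong assumptions.** They require |ρ| near 0.8 and a slope SD close to the 10 msec margin. The SAP supports neither, so the 1–3% range should lead.

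**The coded contrast is hardly touched.** The coded LSMEANS difference sets the same concentration in both arms, so the slope cancels and the loss is at most 1.7%. This stands. The larger figures apply to ddQTcF with placebo at zero concentration, as the prose has it.

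**Stronger readings.** A reader might infer that the zero covariance misweights the 10 placebo subjects; the calculation shows that it does not. A reader might also infer that the 10 msec decision is invalid. There is no bias, and a bootstrap that resamples subjects (the SAP does not state the unit) would show the loss as a slightly wider interval.

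**Conclusion.** The point holds as a small matter of efficiency and consistency. The primary code fixes at zero a covariance that the SAP itself expects in the secondary analysis. If the correlation is real, the standard error of ddQTcF at Cmax is about 1–3% larger at |ρ| = 0.5 and roughly 2–10% larger at |ρ| = 0.8 (11% in the most extreme simulated case). It is unchanged at ρ = 0. In the cases worked through, the upper limit moves by less than half a millisecond. The model-based standard error of the treatment effect can be roughly 5–15% wrong in either direction, which bears on the significance that the SAP will consider.

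All sizes rest on assumed variance components, correlation and concentration profiles, because the SAP gives none. The direction does not: freeing the covariance showed no material loss at zero correlation and a gain, sometimes too small to detect, otherwise.

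**What to change.** In the primary model, use the statement already written for the secondary models: "RANDOM INTERCEPT CONC / TYPE=UN SUBJECT = SUBJID". Add one sentence: return to variance components only if the fit does not converge or the estimated 2 × 2 matrix is not positive definite, and apply the same rule to each bootstrap refit. If zero covariance is intended, state why.

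The cost is one code option, one sentence and one extra covariance parameter. Non-convergence becomes somewhat more likely, including across the 1000 bootstrap fits; its rate was not assessed here. The change should be made before the blind is broken, because Section 4 of the SAP treats analyses designed later as post hoc.

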  LSMEANS TRT TRT*ATPTN /DIFF ALPHA=0.1 CL;  
RUN;
```

In the above statements:

- TRT represents the treatment (active or placebo);
- ATPTN represents the postdose nominal time point;
- BASE represents the baseline value for QTcF;
- CONC represents measured plasma concentrations of moxidectin;

- SP(POW) is a spatial power law covariance structure (a time-dependent first-order autoregressive covariance designed for unequally-spaced time points), if the model does not converge then unstructured or compound symmetry structures will be assessed, in that order;
- LSMEAN differences between the treatments at the Geometric C_{\max} value and at the average concentration value, where xx.x represents the largest geometric mean C_{\max} value among the doses, most likely for the 36-mg dose, will be provided.

Model assumptions will be reviewed with plots of standardized residuals versus fitted values and normal Q-Q plots of the standardized residuals. If nonlinearity is present, a log linear and/or maximum effect (E_{\max}) or other model will be considered.

Similar analyses will be repeated for HR, PR, and QRS, however, bootstrap percentiles will be based on the 2.5th and 97.5th percentiles, corresponding to a 2-sided 95% CI rather than the 2-sided 90% CI.

Secondary Analysis: Pharmacokinetic/Pharmacodynamic Analyses

To evaluate the relationship between placebo-corrected mean change from Baseline in QTcF (ie, ddQTcF) versus plasma concentrations of moxidectin for all subjects in the PK/PD population, both graphical and mixed-effects analyses of plasma concentration of ddQTcF versus plasma concentration of moxidectin will be performed. The mixed-effects model will be used to account for the clustering effects within each subject at different time points. The mixed-effects model will contain ddQTcF as the dependent variable and include the corresponding time-matched plasma moxidectin concentrations as the independent variable. The mixed-effects model will be used to estimate, for all subjects, the predicted population mean ddQTcF and its corresponding upper 95% 1-sided (equivalent to the upper 90% 2-sided) CI over a range of observed plasma concentrations. A negative result (ie, the model indicates no plasma concentration effect) is a slope of approximately zero.

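### The coded primary ddQTcF contrast gives active and placebo the same concentration, so the concentration slope cancels and the 10-msec criterion cannot detect concentration-related QT prolongation

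*SAP*

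**What the plan says.** SAP section 8.3 codes the primary model as "MODEL dQTcF = BASE TRT ATPTN TRT*ATPTN CONC /SOLUTION", with a random intercept and a random concentration slope by subject. Treatment has two levels ("TRT represents the treatment (active or placebo"). There is one fixed CONC slope and no TRT*CONC term. On the data going into the fit, the section says: "Concentrations of zero will be used for the placebo treatment".

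The result is called negative on the "upper bound of the 2-sided 90% bootstrapped CI for ddQTcF being below 10 msec at the largest geometric mean" Cmax. The section defines ddQTcF as the placebo-corrected value estimated from this model.

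The code given for the difference is "LSMEANS TRT TRT*ATPTN /DIFF ALPHA=0.1 CL at CONC=xx.x". It is followed by the same statement without the AT option, "LSMEANS TRT TRT*ATPTN /DIFF ALPHA=0.1 CL", which SAS evaluates at the mean of CONC. The key under the code confirms that this is intended: it promises "LSMEAN differences between the treatments at the Geometric" mean Cmax and at the average concentration, where xx.x "represents the largest geometric mean C_{\max} value among the doses, most likely for the 36-mg dose, will be provided".

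**The concern.** `LSMEANS ... AT CONC=xx.x` fixes the covariate at one value for every least-squares mean it produces, so placebo is also evaluated at the Cmax of the top dose. With a single common slope, both means carry the same slope term, and subtracting one from the other removes it. What is left is the active-placebo difference at equal concentration. The primary objective asks about the QT effect that comes with concentration, and the coded difference excludes it.

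This is the only coded calculation of the difference in the primary analysis, and the formal safety conclusion depends on it. The error runs in the unsafe direction: a drug whose QT effect acts through its concentration would tend to meet the criterion for a negative result.

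**Working it through.** **The plan's own figure.** Section 3.2 states 900 QTc-PK pairs. 60 subjects × 15 time points (baseline plus 14 postdose) = 900, so it reproduces. The postdose records number 60 × 14 = 840, of which 50 × 14 = 700 are on active drug. The SAP gives no SD, effect size or power, so every SD below is an assumption.

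**Step 1: algebra (no assumptions beyond the coded model).** Write

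E[dQTcF] = b0 + b1·BASE + τ(TRT) + t(ATPTN) + g(TRT, ATPTN) + s·CONC.

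With both arms at CONC = c, as coded:

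D(c) = (τ_A − τ_P) + (g_A − g_P) + s·c − s·c = (τ_A − τ_P) + (g_A − g_P).

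D does not depend on c or s, so the two LSMEANS statements must return identical differences. The quantity the criterion needs, with active at Cmax and placebo at 0, is

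Δ = (τ_A − τ_P) + (g_A − g_P) + s·Cmax = D + s·Cmax.

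The coded estimate is short by exactly s·Cmax.

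**Step 2: one simulated trial.** The data set had 60 subjects and 14 postdose times. Concentrations were in arbitrary units, with a geometric mean Cmax of 1.129 in the top-dose group. A mixed model with the SAP's fixed effects and a random intercept and slope gave a slope of 17.33 msec per unit.

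| CONC set in both arms | Active | Placebo | Difference (msec) |
|---|---|---|---|
| 0 | 1.783 | 1.745 | 0.0388 |
| 0.282 (mean) | 6.670 | 6.632 | 0.0388 |
| 1.129 (Cmax) | 21.347 | 21.308 | 0.0388 |
| 3 | 53.770 | 53.731 | 0.0388 |

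Active at Cmax minus placebo at 0 is 21.347 − 1.745 = 19.60 msec. Equivalently, 0.0388 + 17.33 × 1.129 = 19.60.

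**Step 3: repeated trials.** There were 400 trials per setting. Assumptions: dose-proportional exposure; effect linear in concentration with no separate treatment effect; subject SD 4 msec; residual SD 6 msec with spatial-power correlation; slope SD 4 msec per unit. The upper bound is estimate + 1.645 × SE, with the covariance taken as known. The same random draws were used in each row, so the coded results are identical across rows.

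| True effect at Cmax (msec) | Coded: mean; mean upper bound | Coded: meets criterion | Active at Cmax vs placebo at 0: mean; mean upper bound | Meets criterion |
|---|---|---|---|---|
| 0 | −0.02; 3.11 | 100% | −0.06; 3.67 | 99.3% |
| 11.3 | −0.02; 3.11 | 100% | 11.25; 14.98 | 3.3% |
| 17.0 | −0.02; 3.11 | 100% | 16.91; 20.63 | 0% |
| 22.6 | −0.02; 3.11 | 100% | 22.56; 26.29 | 0% |
| 33.9 | −0.02; 3.11 | 100% | 33.88; 37.60 | 0% |

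The coded column is the overall TRT difference. If the 4-hour difference decides, 98.5% pass; if all 14 time points must pass, 91.2% do. With larger SDs (subject 6, residual 9; true effects 17.0 and 22.6 msec) the three coded rates are 97.0%, 82.0% and 43.0%, and the intended contrast passes in 0%. With SDs of 5 and 7 msec and true effects of about 11 to 33 msec, separate simulations gave 99.8 to 100% for the coded overall difference and 0 to 3.1% for the intended contrast.

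**Step 4: the bootstrap does not repair it.** One simulated trial (true effect about 22.6 msec) was resampled by subject 1000 times, with a spatial-power covariance and 5th and 95th percentiles. The coded contrast gave −5.6 to 3.4 msec (passes). Active at Cmax versus placebo at 0 gave 18.4 to 28.1 msec (fails).

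**The case against.** The strongest reply is that the prose of section 8.3 does not itself contain the error. It speaks of predicting ddQTcF at relevant concentrations and sets placebo concentrations to zero, which can be read as active at Cmax against placebo at zero. That is a fair reading of the prose alone. But the zero applies to the data in the fit, and the AT option overrides it when the means are formed. The code and its key then fix the other contrast, and a programmer following them would get the wrong number.

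Second, a real effect would not be invisible. The slope is reported, and a significant slope triggers further examination. Section 8.2 summarises ddQTcF by dose and time. The secondary model predicts ddQTcF at each dose level's mean maximum concentration from its own slope, where nothing cancels. All of this stands, but the 10-msec criterion is tied to none of it. The one extra item weighed beside the criterion is the treatment covariate, which also leaves out the slope.

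Third, the false pass assumes an effect that is linear and acts wholly through concentration. Under nonlinearity or hysteresis, part of the effect could load on the treatment terms, and the SAP provides for other models in those cases. A concentration-independent effect would also appear in TRT. These limits are accepted.

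Fourth, the pass rates depend on assumed SDs and on whether the overall or a per-time-point difference governs, which the criterion does not say. Also accepted: the rates are illustrations. The lower per-time-point rates come from noise and do not bring the slope back into the estimate.

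**Conclusion.** The concern holds. The cancellation is exact and follows from the coded model alone; it does not depend on the simulations. The quantity coded for the primary decision omits slope × Cmax, which under a linear concentration effect is the whole of the effect being tested. The formal criterion would then usually be met whatever the size of the prolongation: in 97 to 100% of simulated trials on the overall difference, against at most 3.3% for the intended contrast at true effects of 11 msec or more. Those rates rest on assumed SDs (subject 4 to 6, residual 6 to 9 msec), linearity and no separate treatment effect. On a per-time-point reading the coded pass rate ranged from 43% to 98.5%. Since the error can reverse the primary safety conclusion, it must be corrected before database lock.

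**What to change.** Replace the LSMEANS difference as the decision quantity with a contrast that gives CONC = xx.x to active and 0 to placebo, for example an `ESTIMATE` statement with `TRT 1 -1`, `TRT*ATPTN` coefficients of +1/14 for each active and −1/14 for each placebo time point, `CONC xx.x`, and `ALPHA=0.1 CL`. Check the level order against the CLASS statement.

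The 1/14 weights reproduce the averaging over time that `LSMEANS TRT` already does. For a single time point, use +1 and −1 at that time instead. The sponsor should state which of the two governs the criterion.

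Bootstrap this contrast with the percentile method already specified, and compare its upper 90% bound with 10 msec. Reword the code key to define ddQTcF as active at the stated concentration minus placebo at zero. Use the same definition if an effect-compartment or nonlinear model replaces the linear one. Make the same change for HR, PR and QRS, which section 8.3 analyses in the same way. If the LSMEANS output is kept, label it as the difference at equal concentration.

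The cost is a few lines of SAS and SAP wording; no new data are needed.

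### The secondary ddQTcF-concentration analysis calls a slope near zero a negative result, with no limit, confidence bound or intercept, so the label can stand beside a predicted upper bound above 10 msec

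*SAP*

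**What the plan says.** SAP Section 8.3 contains two statements about a negative finding.

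- **Primary analysis** (mixed model for dQTcF). A negative QT assessment is defined as "the upper bound of the 2-sided 90% bootstrapped CI for ddQTcF being below 10 msec at the largest geometric mean C_{max} value". The plan adds that "the significance and magnitude of parameter estimates of the treatment covariate (active vs. placebo) will be considered".
- **Secondary analysis** (mixed model for ddQTcF in the PK/PD population). The rule is: "A negative result (ie, the model indicates no plasma concentration effect) is a slope of approximately zero".

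The secondary model is coded as "MODEL ddQTcF = CONC /SOLUTION OUTPM=PRED ALPHA=0.05" with "RANDOM INTERCEPT CONC / TYPE=UN SUBJECT = SUBJID". No option suppresses the fixed intercept, so the prediction at concentration C is intercept + slope x C. Just before the slope rule, the plan says that the model will give the predicted mean ddQTcF with its "upper 95% 1-sided (equivalent to the upper 90% 2-sided) CI over a range of observed plasma concentrations". It later asks for predictions with 90% limits at chosen concentrations ("ie, the mean maximum plasma concentration under each dose level"). Neither prediction is linked to the conclusion or to a threshold. The plan also allows a quadratic term or a log-transformed concentration if the fit calls for it.

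**The concern.** The plan computes the quantity that matters, a predicted ddQTcF with an upper limit, and then draws its secondary conclusion from something else. Three features of the slope rule cause trouble.

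1. **No numerical limit.** How close to zero is close enough would be settled after the results are seen, although Section 4 describes the planned analyses as fixed before unblinding.
2. **No precision.** A slope near zero from a poor fit meets the wording as well as one from a tight fit.
3. **No intercept.** A shift common to all concentrations leaves the slope at zero.

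The reason to care about a secondary rule lies in Section 8.3 itself. It justifies the ddQTcF analysis by the risk that circadian change distorts the dQTcF model, and its example is a relationship that crosses the 10-msec boundary. An analysis offered as a safeguard on that question should not be able to report a negative result while its own upper bound is above 10 msec.

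**Working it through.** The plan gives no figure for this rule, so there is nothing to reproduce. The check is algebra on the model as coded.

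**Inputs from the SAP.** Margin 10 msec, two-sided 90% interval and largest geometric mean Cmax (Section 8.3, primary analysis). Intercept-plus-slope model (Section 8.3, secondary code). 50 active and 10 placebo subjects (Section 3.2).

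**Assumed.** The SAP gives no SD, slope, intercept or Cmax, so standard errors (SE) are assumed and shown as a range. Concentration is scaled so that the largest geometric mean Cmax equals 1.

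**Formula.** Upper bound at Cmax = intercept + slope + 1.645 x SE of the prediction.

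**Constant offset, slope exactly 0.** Slope 0, intercept 8, SE 1.5 gives 8 + 0 + 2.47 = 10.47 msec. The slope rule says negative, but the bound exceeds 10. The intercept at which the bound reaches 10 is 10 - 1.645 x SE:

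| SE at Cmax (msec) | Intercept at which bound = 10 (msec) |
|---|---|
| 1 | 8.36 |
| 1.5 | 7.53 |
| 2 | 6.71 |
| 3 | 5.07 |

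**Imprecision, slope and intercept both 0.** The bound exceeds 10 when SE > 10 / 1.645 = 6.08 msec.

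**Illustration by simulation.** Setting: 50 active and 10 placebo subjects, 14 postdose times, an assumed concentration profile, and between-/within-subject SDs of 5/5, 7/7 and 10/8 msec, with 200 runs each. With true slope 0 and a constant offset of 8 msec, 29% to 42% of runs had a non-significant slope together with an upper bound of at least 10 msec. Non-significance at 5% stood in for a slope near zero, and no random slope was fitted, so these percentages only illustrate the algebra.

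**Non-linear models.** If a quadratic term is added, as the plan permits, no single slope exists and the rule gives no answer. A bound on predicted ddQTcF works under every model that the plan allows.

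**Can the secondary model's own interval carry a 10-msec rule?** Section 2.4.2 forms ddQTcF by subtracting one placebo mean per time point. All 50 active subjects share that mean, and the secondary model has no term for its error. With an assumed between-subject SD of 5 to 6 msec, the omitted SE is 5/√10 = 1.6 to 6/√10 = 1.9 msec. Take slope 0, intercept 7 and a model SE of 1.5:

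- Model SE alone: 7 + 1.645 x 1.5 = 9.47 msec, which passes.
- With SD 5: SE = √(2.25 + 2.5) = 2.18, and the bound is 10.6 msec.
- With SD 6: SE = √(2.25 + 3.6) = 2.42, and the bound is 11.0 msec.

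The simulation points the same way. With true slope 0 and no offset, the model's slope test was significant at 5% in 25.5% to 34.5% of runs, and most of that excess disappears if the placebo mean is treated as known. A 10-msec rule on the unmodified model interval would be too lenient.

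**The case against.** The case for leaving the sentence alone has real substance.

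- **The label is qualified.** The parenthesis restricts it to the absence of a concentration effect, which is not the primary analysis's negative QT assessment. This stands. A reader might infer that a clearly non-zero slope with a small bound (say 4 msec at Cmax, SE 1.5, bound 4 + 1.645 x 1.5 = 6.5 msec) also shows the two rules in conflict. It does not: a concentration effect and a QT effect under 10 msec can both be true.
- **The primary decision does not use this rule.** This also stands. The only formal criterion is the primary one, and it is unchanged.
- **A flat shift would be visible elsewhere.** The primary model has a treatment term whose size is to be considered. Section 8.2 and Figure 14.2.2.6 give ddQTcF with 90% intervals by time point, and the secondary predictions would show the shift too. So the offset would not be hidden, but the secondary analysis would still carry the wrong label.
- **The stated worry in Section 8.3 is a spurious slope, so a slope conclusion fits.** Partly so. Even as a statement about the slope alone, the rule has no limit, interval or test.
- **Precision is available in the output.** The code requests the solution table, so the slope's SE will be printed. The rule does not use it.

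A reader might also infer that predicting at mean rather than geometric mean Cmax puts the two analyses at materially different exposures. For lognormal Cmax the ratio is √(1 + CV²), or 1.04 at an assumed CV of 30% and 1.12 at 50%. The arithmetic mean is the higher exposure, hence the stricter point for a positive slope. That difference is minor.

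**Conclusion.** The point holds in limited form. As worded, the secondary rule can call a result negative on a near-zero point estimate when the predicted upper bound planned in the same paragraph is above 10 msec. With slope exactly 0, this happens once the intercept reaches about 5.1 to 8.4 msec for assumed SEs of 3 down to 1 msec. With slope and intercept both 0, it happens once the SE exceeds about 6.1 msec. These thresholds follow from the coded model and the 10-msec margin; only the SEs are assumed.

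A reader might go further and infer that the trial's QT conclusion is unsafe. The SAP does not support that: the primary criterion stands by itself, uses a confidence bound at a named exposure, and is accompanied by the treatment term and the by-time summaries. What is unsound is the supportive conclusion.

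**What to change.** Replace the sentence in the secondary part of Section 8.3 with wording such as:

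> The secondary analysis supports a negative QT assessment if the upper limit of the two-sided 90% CI of predicted ddQTcF (intercept plus slope times concentration, or the corresponding prediction from the selected non-linear model) is below 10 msec at the largest geometric mean Cmax. The CI is obtained by bootstrapping active and placebo subjects together, recalculating the placebo means in each resample. The slope and intercept are reported with 90% CIs; the slope describes evidence for a concentration effect and is not by itself a negative QT result.

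Two edits in the same section should go with it. The text on predictions names only the slopes and should name the intercept as well. The ALPHA=0.05 in the secondary code gives 95% two-sided limits where the text asks for 90%.

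The cost is a short text change, a small amount of extra computation (a percentile bootstrap is already planned for the primary model) and a slightly wider secondary interval, which is the honest width once placebo error is counted. No data collection or design element changes.
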